4.1 Selection of the Study Population

Our trial will focus on the pediatric population. **Specifically, children 2-15 years of age at the time of enrollment living within the assigned clusters in the city of Merida, Yucatan, Mexico.** Briefly, the FSD cohort indicated that the majority of dengue naïve infections and seroconversions were observed in children <15 years old^{47,49,50} (Fig 6) and, while they had lower symptomatic illness than adults, the chances of detecting both infection and disease is expected to be higher than older age groups due to their lower natural immunity to ABVs. CHIKV and ZIKV incidence during the first wave of their invasion into the Yucatan was also larger in the <15 year-old group (Table 2), supporting our age-group eligibility criteria. We will exclude younger children (<2 years) because of the inherent difficulties obtaining blood from small children, and potential for cross-reactivity of maternal antibodies⁶³.

[figure not shown]

Fig. 6. Age-specific baseline dengue seroprevalence in Merida cohort, Yucatan, Mexico. From [Rojas et al.

	Person-years at risk (N)	Dengue	IR (95%CI)	Chikungunya	IR (95%CI)	Zika	IR (95%CI)
All participants	3430.9 (3400)	12	3.5 (1.9, 5.9)	30	8.6 (5.8, 12.3)	8	2.3 (0.9, 4.5)
Age groups (years)							
≤ 8	1001.4 (991)	3	2.9 (0.6, 8.8)	10	9.9 (4.8, 18.4)	4	3.99 (1.1, 10.2)
9-14	502.5 (484)	1	1.9 (0.03, 11.1)	4	7.9 (2.1, 20.4)	2	3.9 (0.5, 14.4)
15-19	145.3 (146)	1	6.88 (0.1, 38.3)	1	6.9 (0.1, 38.3)	0	0
20-49	1490.1 (1456)	7	4.7 (1.9, 9.7)	11	7.4 (3.7, 13.2)	2	1.3 (0.2, 4.9)
≥ 50	291.5 (323)	0	0	4	13.7 (3.7, 35.1)	0	0
Gender							
Male	1511.7 (1531)	0	0	9	5.9 (5.8, 12.3)	3	1.9 (0.4, 5.8)
Female	1919.2 (1869)	12	6.3 (3.2, 10.9)	21	10.9 (6.8, 16.7)	5	2.6 (0.8, 6.1)

Table 2. Incidence rates (IR) per 1,000 person-years of arbovirus confirmed symptomatic infections in the cohort in Yucatan, Mexico by age, gender. Extracted from Rojas et al. 2018⁵².

There will be no exclusion criteria related to gender, ethnic or racial category. While females had slightly higher rates of ABV incidence than males (Table 2), our trial will enroll both male and female children. The health status of this population at enrollment will be mostly healthy. Based on our FSD cohort studies, we expect to enroll 50% females, and Mexican citizens, Spanish speakers, and of mestizo ethnicity (mixed Mayan and white/European). The health status of this population at enrollment will be mostly healthy.

While our study will include participants of both sexes, our analysis plan will not use such information to assess the primary or secondary endpoints and quantify the epidemiologic impact of TIRS. We will recruit 4,600 children aged 2-15. Our team has vast experience working with children as part of our FSD cohort study^{47,49,50}. Our team of four physicians will include an

infectious disease pediatrician ([name]), who has extensive experience (~30 years) diagnosing infections locally circulating in Merida, including ABVs. Table 3 shows the sample size and procedures that will be followed for each segment of the population.

Study Component	Target N (expected or planned)	Activities
Febrile Surveillance	4,600	Census, household visits 1x/wk, phone calls 2x/wk. for two transmission seasons (and potentially 3).
Probable acute ABV illness. (From active surveillance)	1,000	2 blood samples (acute and convalescent, 14-30 d after acute) to all cases meeting the ABV case definition. Demographic and movement interviews at first visit.
Serosurvey	4,600	Provide a blood sample 1/yr for two years (and potentially 3) to quantify ABV exposure.
Loss to follow-up interviews	920	Interview participants leaving the study to assess potential causes.

Table 3. Target sample size of children aged 2-15 at the time of enrollment, and activities performed on them.

4.2 Inclusion/Exclusion Criteria

There will be two levels of participation in the trial: 1) at the household level, owners will consent to have their house sprayed with TIRS; 2) at the individual level, children 2-15 years of age at the time of enrollment will consent/assent to participate in the study, which will require their prospective follow-up for signs of ABD illness and yearly blood draws to assess seroconversion. The inclusion/exclusion criteria for each level is as follows:

1. Household Level

1.1. Inclusion Criteria:

- Household is located within the bounds of a study cluster (5x5 city-block clusters).
- City block has at least 60% premises that are residential.

1.2. Exclusion Criteria:

- Households where study personnel identify a security risk (i.e., site where drugs are sold, residents are always drunk or hostile)
- Sites where no residents spend time during the day (i.e. work 7d a week outside the home).Inability for a resident to provide informed consent.
- Non-residential places (e.g., businesses, schools, markets, etc.).

2. Individual Level

2.1. Inclusion Criteria:

- 2 or more and up to 15 years of age at the time of initial enrollment
- Living in a house that consented to TIRS.

2.2. Exclusion Criteria:

- Less than 2 years of age or more than 15 years of age at the time of enrollment.
- Not living in a house that consented to TIRS.

- Having a medical condition that prevents implementation of study procedures.
- Temporary visitor to household
- Plans to leave study area within next 12 months

5 STUDY PROCEDURES/EVALUATIONS

5.1 Study Procedures

See manual of procedures attachment for detailed procedures and forms for each component.

Intervention: Personnel from CENAPRECE with experience performing indoor residual spraying and trained to apply TIRS will conduct the spraying which --based on our model predictions-- should start between May 1st and June 1st and extend for 1.0-1.5 months. *Ae. aegypti* in Merida and Yucatan are susceptible to both carbamates and organophosphates. Either Ficam® (Bayer, a carbamate) or Actellic 300CS® (Syngenta, an organophosphate) will be used on a given year to treat all houses. We will prioritize the use of Actellic 300CS®, given its longer residual power in comparison to Ficam® (7-8 months versus 4-5 months, respectively). However, if insecticide resistance profiles of mosquitoes at baseline or after the first year of spraying show decreases in susceptibility to Actellic 300CS®, we will switch to Ficam®. Insecticide application will follow strict SOPs developed by our team as part of a CDC-Emory-UADY collaboration (see Manual of Procedures). Each spraying team will include 2 spraymen and one supervisor in charge of communicating with the household owners and evaluating the quality of spraying. Team leaders will ask the homeowner if there are areas or rooms they do not wish to have treated (and take note in the field spraying form). Residents will be asked to temporally leave the room during treatment and wait at least 30 minutes for the product to dry before re-entering the home. We will avoid treating near pets, especially near fish tanks, and do not spray children's toys, food, kitchens or exposed cloths and bedding. Staff will wear branded uniforms with identification at all times and use appropriate personal protective equipment (Fig. 1 in Research Strategy document). Relevant treatment data will be captured in the field using smartphones connected to the project's REDCap database.

Blood Samples: Venipuncture procedures will be performed using standard aseptic techniques. An experienced phlebotomist will take the blood sample from an antecubital vein. Blood volumes will depend on the participant's age (5 ml for children under 8 years and 10 ml for children 9-18 years). Blood will be collected into Vacutainer® collection tubes or by a needle and syringe. A 22-gauge needle will be used for 5-15 yr olds, and a 23-gauge needle for children <5 yrs. Serum will be separated and stored at -70°C in labeled polypropylene cryogenic vials. When results are available they will be provided to individual study participants with an explanation of their significance. We have found in previous studies that participants are curious about their results even though results often have no impact on treatment.

Entomological Surveys: *Aedes aegypti* surveys will be carried out once per month and for a period of 6 months post-TIRS application in a random sample of 10% of the households participating in the trial (equaling to ~1,600 houses per sampling period). To maintain quality control, an entomological supervisor will accompany the survey team and a second supervisor will review data daily. Adult captures: Adult *Ae. aegypti* will be collected with Prokopack® aspirators 26 and used to calculate six adult indices: prevalence and abundance of adults, females and bloodfed females.

Movement surveys: Two movement surveys will be implemented (see Manual of Procedures). The retrospective movement survey (RMS) obtains information about locations visited in the past 15 days. The RMS gathers information on the main activity performed in visited locations and the self-reported duration of the visits (frequency and time of visits). The RMS will be used to quantify the proportion of time a symptomatic individual spent within their respective cluster and identify potential contamination in the trial by pinpointing to participants who live in one cluster type (e.g., TIRS) and visit other cluster type (e.g., control). We will apply prospective movement surveys (PMS) to all subjects at the time of the yearly serosurveillance blood samples. These surveys ask questions about the routine movements, rather than prior 15 days, and will be used to quantify the cumulative time under treatment for each child. For children up to 8 years, parents are interviewed to ask about time in home and specific places visited, whereas children 9 and up are interviewed directly by our skilled team of anthropologists. The project PI, [name], has over 10 years' experience applying and analyzing RMS and PMS instruments.

5.2 Laboratory Evaluations

5.2.1 Laboratory Evaluations/Assays

Laboratory testing will be shared between UADY and Emory as described below.

Active (enhanced) surveillance: acute samples from suspected ABV meeting our case definition will be tested at UADY using molecular testing by multiplex reverse transcriptase-polymerase chain reaction (RT-PCR) [50], NS1 detection and virus-specific IgM testing. Acute and convalescent specimens will be shared in parallel with Emory for assessment of IgM and IgG seroconversion. Testing of acute specimens in real time on site at UADY is critical as it allows immediate feedback to be given to subjects and/or their medical providers which may impact their clinical care.

Annual serologic surveillance for total ABV infection will be accomplished by obtaining a single serologic specimen from each subject each year of the study, including a baseline specimen prior to commencement of the TIRS intervention and following the final transmission season of the study (Fig 5). Testing will be performed at Emory University by a stepwise testing approach. Each ABV is considered independently – for serosurveillance, each serotype of DENV is considered as a distinct virus. Once an infection is detected, no further testing for infection by that virus is pursued in subsequent study years. Antigen capture ELISA for human IgG[51] will be the first test. Conversion from negative to positive for IgG indicates interval infection. Measurement of neutralizing antibody by focus reduction neutralization testing (FRNT) will provide a confirmatory and, in some cases, a more specific serologic assay [52, 53, 54]. For flaviviruses, seronegatives will be tested each year by IgG ELISA [55]. The first positive IgG ELISA to DENV or ZIKV will trigger FRNT testing to determine immunity to specific viruses. For flavivirus IgG positive subjects, further assessment for interval infection will rely solely on FRNT testing. CHIKV IgG conversion will be confirmed with neutralization testing by FRNT.

Mosquito Infection: The low indoor density of *Ae. aegypti* [48, 56] would make it too costly to quantify ABV infection at the household level. Therefore, we will quantify natural ABV infection

rates in *Ae. aegypti* at the city block level (9 blocks per cluster * 50 clusters = 450 blocks monitored monthly). At the UCBE lab, we will pool all female *Ae. aegypti* collected in a block in vials containing 25 mosquitoes (if more than 25 females are collected in a city block, we will make more than one vial). Vials will contain RNALater (Qiagen) and will be stored at -80°C for future testing, which will occur at the end of each transmission season (January-June). RNA will be extracted with an QIAamp Viral RNA kit (QIAGEN, 52904). We will implement RT-PCR procedures [50] for ABV detection using a StepOne Plus (Applied Biosystems) thermocycler.

Insecticide Resistance. Standard CDC bottle bioassays [57] will assess phenotypic resistance of adult *Ae. aegypti* from treatment and control clusters pre-spraying and at 3 and 9 months post-spraying every year. We will generate 10 *Ae. aegypti* colonies using eggs collected from 10 randomly selected clusters (5 intervention and 5 control). F1 or F2 progeny from each colony will be screened for susceptibility to the following insecticides: deltamethrin, bendiocarb and pirimiphos-methyl using the diagnostic doses (DD) and diagnostic times (DT) previously established for *Ae. aegypti* by the CDC [57]. When resistance is detected, both DNA and RNA will be analyzed from a subset of the phenotyped mosquitoes to calculate the frequencies of known resistance alleles as well as expression of resistance-associated genes. This will enable us to measure changes in resistance mechanisms over time and in response to insecticide pressure. All resistance typification activities will occur at the Entomology lab at CDC in Atlanta, GA.

5.2.2 Specimen Collection, Preparation, Handling and Shipping

5.2.2.1 Instructions for Specimen Preparation, Handling, and Storage

Special instructions for the collection, labeling, preparation, handling, and storage of specimens are detailed in the Manual of Procedures attachment.

5.2.2.2 Specimen Shipment

We will be shipping serum samples from UADY to Emory for advanced and confirmatory serological assays. We estimate such shipments to occur 2x/year, coinciding with the end of the transmission season and the end of the annual sero-survey. Also, we have included *specific SOPs in the Manual of Procedures for handling blood specimens*. Mexico allows human specimen sample export to the US as long as a permit is signed by COFEPRIS (the Mexican equivalent to FDA). Approvals are protocol-specific, and we will be submitting paperwork specifically for this study.

6 STATISTICAL CONSIDERATIONS

6.1 Study Outcome Measures

Outcome measures are summarized in the following table:

Type	Name	Time Frame	Brief Description
Primary	Laboratory-confirmed	Post-treatment	Laboratory-confirmed (virologically [RT-PCR testing of acute samples] or serologically [IgM and IgG ELISA testing of paired acute and convalescent samples]) symptomatic DENV, CHIKV or ZIKV.
Secondary	Laboratory confirmed	Post-treatment	Laboratory confirmed (serologically, [IgG ELISA and neutralization testing of annual surveillance samples]) DENV, CHIKV or ZIKV infection
Secondary	Aedes aegypti infection	Post-treatment	Ae. aegypti mosquito infection rates with DENV, CHIKV, ZIKV (assessed by RT-PCR)
Secondary	Aedes aegypti infestation	Post-treatment	Ae. aegypti indoor entomological indices (adult presence and abundance, female presence and abundance, bloodfed female and abundance)
Secondary	Community acceptance	Post-treatment	Percentage of households receiving the intervention that would recommend it to others in the community (assessed by household surveys)
Secondary	Safety profile	Post-treatment	Percentage of households receiving the intervention that had evidence of a reaction to the insecticide (assessed and confirmed by study doctors)

The primary endpoint will be binary (infected yes/no) and will be used as is for the Cox proportional hazards model. Additional variables will include date of onset of symptoms as well as house and cluster ID. No transformations will be made on such variables.

For secondary endpoints, epidemiological data will also be binary (interval seroconversion, which is the combined assessment of the serological status of a participant between annual serosurveys) and used in logistic models without transformation.

For infection in mosquitoes, we will collect binary data (a mosquito pool is either infected or not), and transform it into minimum infection rates (MIR): $(1/\# \text{ mosquitoes in the pool}) * 1,000$. This measure assumes that, when a pool is positive, it was due to at least one mosquito. That is why it is called 'muminimum'.

For mosquito collections, data will be collected as counts (number per house) and used as is for negative-binomial analysis or used to calculate infestation (binary at the house level, with a house being infested or not). Both measures will be used as described in [34].

We will perform household surveys to assess the acceptability of the intervention for those households receiving it. We will quantify the % of heads of household that would recommend the intervention to others.

Upon receipt of a sign of potential health reaction to insecticides used, doctors will visit the household and assess whether it could be related to the application. The % of households reporting signs of potential intoxication will be quantified for houses receiving the intervention.

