Planned secondary analyses of clinical and human serological data include:

- Cox proportional hazards model with time to first laboratory-confirmed symptomatic ABV disease as the endpoint, adjusting for additional cluster- and household-level covariates (e.g. population density, household size, socio-economic status).
- Cox proportional hazards model with time to first laboratory-confirmed symptomatic ABV disease as the endpoint, adjusting for routine human movement as measured by the prospective movement survey (measured in all enrolled participants). The proportion of time in treated areas will be included as a further covariate.
- Disease-specific versions of the primary analysis (e.g. time to first laboratory-confirmed symptomatic dengue disease as the endpoint), if data permit.
- Analysis of recent human movements measured by RMS in enrolled participants presenting with symptoms for laboratory confirmation. The data will be analyzed using a test negative design-type structure, where individuals testing negative for any ABV will

serve as a comparator group for individuals testing positive for ABV. The analysis will adopt recently developed methods for cluster randomized vector control trials ⁸¹.

- Binomial generalized linear mixed effects model to assess the efficacy of TIRS for reducing laboratory-confirmed DENV, CHIKV, or ZIKV infection, analyzed as cumulative incidence over the two (or potentially three) transmission seasons, as measured from annual serological samples.

Entomological endpoints:

Planned secondary analyses of mosquito data include:

- *Ae. aegypti* indoor entomological indices (adult presence and abundance, female presence and abundance, blood fed female presence and abundance) and ABV minimum infection rates (# infected mosquitoes/total mosquitoes tested x 1,000).
- Negative binomial GLMMs will test for differences in treatment and control arms for all entomologic indices as in our previous work, including *Ae. aegypti* infection rates with DENV, CHIKV, or ZIKV, and *Ae. aegypti* indoor entomological indices (adult presence and abundance, female presence and abundance, blood fed female presence and abundance) [34].

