- The following *Ae. aegypti* adult indices will be calculated for each sampling date and compared between treatments and over time: presence (binomial variable) and abundance (count variable) of adults, females and bloodfed females per house. Generalized linear mixed effects models (GLMM) nested at the cluster (level 1) and city-block (level 2) levels will be used to compare each entomological index between treatment and control arms. Link functions for GLMMs will be binomial for presence indices and negative Poisson for abundance indices. The best fit models (after comparing AIC values for models including all levels or only Level 1) will be used to calculate odds ratios (OR, for mosquito presence/absence) and incidence rate ratios (IRR, for mosquito abundance) using control houses as the unit of comparison. We will calculate the operational efficacy of the intervention as $E=(1-IRR) \times 100$. This measure, ranging between 0 and 1, describes the percent reduction of mosquito abundance in treated houses with respect to the control. All models will be run with the software package lme4 within the software platform R (<https://www.r-project.org/>).

Transmission modeling

Our existing mathematical model for Yucatan[35, 59] will be used to simulate the effectiveness of TIRS for different scenarios of intervention coverage and insecticide residual power, using the observed trial data as a critical model input. This agent-based model of individual people and mosquitoes incorporates household demography, a spatially heterogeneous population structure based on census and remote sensing data, movement of workers and students, and seasonal fluctuations in mosquito population and incubation period.

We will model TIRS in treated households as (1) reducing the location's susceptible mosquito population and (2) increasing daily mortality probability for infected mosquitoes. For computational efficiency, we represent susceptible mosquitoes probabilistically and infected mosquitoes explicitly. For (1) we use the TIRS efficacy to reduce the susceptible population, and for (2) we calculate a daily additional mortality probability associated with the overall population reduction (e.g. roughly 0.13 for 80% efficacy TIRS). This additional mortality is treated separately from the normal daily mortality due to age or other factors. To calculate daily mortality, we use the assumed TIRS efficacy combined with our empirically-derived model for

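### Mosquito infection endpoint: a negative binomial model does not fit a minimum infection rate, and neither the model's row unit nor an offset is stated

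*Combined protocol and SAP*

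**What the plan says.** Section 5.2.1 measures infection by city block because low indoor density "would make it too costly to quantify ABV infection at the household level". Females are pooled by block in vials of up to 25, with "9 blocks per cluster * 50 clusters = 450 blocks monitored monthly".

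Section 6.1 then says of the pool results: "we will collect binary data (a mosquito pool is either infected or not), and transform it into minimum infection rates (MIR"), with 1,000 divided by the number in the pool as the formula. Section 6.4 gives a second formula: "ABV minimum infection rates (# infected mosquitoes/total mosquitoes tested x 1,000").

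For the test, section 6.4 states: "Negative binomial GLMMs will test for differences in treatment and control arms for all entomologic indices as in our previous work, including" infection rates with the three viruses. The next bullet nests the mixed models "nested at the cluster (level 1) and city-block (level 2) levels" and adds: "Link functions for GLMMs will be binomial for presence indices and negative Poisson for abundance indices". No family is given there for infection rates. Section 6.1 links the negative binomial to a different variable, mosquito collections, where "data will be collected as counts (number per house) and used as is for negative-binomial analysis".

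**The concern.** A negative binomial is a distribution for counts. The response named for this endpoint is a 0/1 pool result divided by pool size and multiplied by 1,000. No count response is named, and no log(mosquitoes tested) offset. As written, the plan fits a count likelihood to a scaled rate, and its standard error then depends on an arbitrary choice of units.

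The row unit of the model is also open. Section 6.1 points to one value per pool and section 6.4 to a ratio of totals over an unnamed unit, and the two weight pools differently. At stake are the confidence interval, the p-value and the power for one secondary endpoint.

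**Working it through.** **Inputs.** From the documents: 9 × 50 = 450 blocks a month, which reproduces the stated figure; pools of at most 25 (5.2.1); about 1,350 houses a month (section 3), so 1,350/450 = 3.0 houses per block-month (1,600/450 = 3.6 on the section 5.1 figure); two seasons of six monthly rounds; an average 74% reduction in females in the earlier pirimiphos-methyl trial (1.1). The documents give no figure for catch per block, its dispersion, infection per mosquito or variation between clusters. These are assumed below.

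**Step 1: the two formulas.** Take positive pools of 3 and 6 and a negative pool of 10. The mean of the pool values is (333.3 + 166.7 + 0)/3 = 166.7. The ratio of totals is 2/19 × 1,000 = 105.3.

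**Step 2: mean and variance of pool-level MIR.** Let π be the infection probability per mosquito and m the pool size. MIR is 1,000/m with probability 1 − (1 − π)^m, and otherwise 0.
- The mean is [1 − (1 − π)^m] × 1,000/m, about 1,000π. At π = 0.01 it is 10 for m = 1 and (1 − 0.7778) × 40 = 8.9 for m = 25. It depends little on pool size, so the ratio between arms is nearly unbiased even though TIRS should make pools smaller.
- The variance is about 1,000² × π/m. A positive pool of 1 scores 1,000 and a positive pool of 25 scores 40, so value and spread both follow pool size.

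**Step 3: why the standard error is wrong.** Suppose every pool holds 3 females and π = 0.01. A share p = 1 − 0.99³ = 0.0297 is positive, and MIR is 0 or 333.3, with mean μ = 9.90. The true variance of the log mean is (1 − p)/p = 32.7 per row. The model uses 1/μ + α. With nearly all rows zero, maximum likelihood sets α close to the value that reproduces the share of zeros, (1 + αμ)^(−1/α) ≈ 0.970, not the variance. Fitted values:

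| Multiplier | μ | α | 1/μ + α | Model SE / true SE |
|---|---|---|---|---|
| 100 | 0.99 | 168.4 | 169.4 | √(169.4/32.7) = 2.28 |
| 1,000 | 9.90 | 257.8 | 257.9 | √(257.9/32.7) = 2.81 |
| 10,000 | 99.0 | 342.5 | 342.5 | √(342.5/32.7) = 3.24 |

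The data are the same in each row; only the units change.

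**Step 4: simulation.** Set-up: 50 clusters × 9 blocks × 12 months, pools capped at 25, 74% fewer females under TIRS, MIR rounded so that the negative binomial can be fitted. With catch dispersion 1, infection 10 per 1,000 and no variation between clusters, power for a true halving of per-mosquito infection is:

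| Control females per block-month | Negative binomial, pool rows | Negative binomial, cluster rows | Pool positivity, complementary log-log |
|---|---|---|---|
| 2 | 6% | 26% | 35% |
| 4 | 19% | 51% | 72% |
| 8 | 53% | 92% | 97% |

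Under the null, model SE over actual SD is 1.6–2.1 with pool rows (rejection 0–0.5%) and 1.03–1.33 with cluster rows (rejection 2.5–7%).

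A wider grid used control means 1, 2, 4 and 8; Poisson catch or dispersion 1 or 0.5; infection 5 or 10 per 1,000; and between-cluster log-SD 0 or 1 (4 × 3 × 2 × 2 = 48 scenarios, 200 null and 100 alternative trials each). For pool rows:
- The null median ratio is 0.92–1.09. SE/SD has median 1.77 (range 0.92–2.39). Null rejection averages 1.2% (0–7.0%).
- At means 4 and 8 with log-SD 0, power is 20% and 38%, against 59% and 83% for complementary log-log. With log-SD 1 it is 22% and 37%, against 28% and 37%. At mean 1 both are about 5% or less.
- Per 100, 1,000 and 10,000, the ratio is unchanged but average power is 28%, 17% and 12%.
- Adding a cluster intercept does not repair it. In 1,433 fits the cluster SD was below 0.03 in 95.5%, and the standard error was within 1% of the plain fit in 95.6%.

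lme4, the package named in section 6.4, was not run.

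**The case against.** - **The level is stated.** A reader might infer that the plan is silent on level. It is not: sections 3 and 5.2.1 give the city block, monthly, and section 6.4 nests by cluster and block. This stands. Only the row unit of the MIR model is open.
- **The negative binomial sentence is loose.** It also covers presence indices, which the next bullet makes binomial. Positive-pool counts with a log(tested) offset would be sound and are not excluded, and the cited earlier work cannot be read here. This stands in part. But the endpoint is defined as MIR, no count or offset is named, and no later sentence corrects the family for infection rates as one does for presence.
- **Non-integer values are a side issue.** 1,000/m is an integer for only 8 of the 25 pool sizes, but most recorded values will be zero. This stands, and the argument does not rest on it. The problem is a scaled rate whose variance follows pool size.
- **The harm depends on assumptions.** Rounding is needed to fit the model and is not in the plan. Cluster rows are much closer to valid, and variation between clusters shrinks the gain. This stands and limits the size of the point.
- **The abundance effect might pass for an infection effect.** A reader might infer this, since TIRS should cut catches. It would need an analysis of positive pools with no denominator. Both formulas divide by mosquitoes, and the documents state no such analysis.

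**Conclusion.** The planned likelihood does not suit the stated response, and the row unit and the two MIR formulas need settling. The point is minor to moderate.

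The scale dependence follows from the negative binomial variance and needs no assumption about the data beyond sparse positives. The size of the loss does rest on assumed catch, dispersion, prevalence and between-cluster variation. With pool rows and little variation between clusters, intervals are too wide and power falls well below what the same pools could give. With cluster rows the loss is smaller; with strong variation between clusters it is small or nil.

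A reader might go further and infer a biased TIRS effect or a general excess of false positives. The documents do not support that: both formulas use mosquitoes tested as denominator, the ratio is then about unbiased, and with pool rows the test is conservative in most assumed scenarios. The primary endpoint, the sample size and the continuation rule are untouched.

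**What to change.** Keep one MIR definition, positive pools divided by total mosquitoes tested × 1,000 by arm, as a descriptive summary. Replace the negative binomial model for this endpoint with wording such as:

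> Pool positivity (0/1) will be analysed with a binomial GLMM with complementary log-log link, offset log(pool size), a fixed effect for arm and a cluster random intercept. A city-block intercept will be added only if it can be estimated. The exponentiated arm coefficient is the per-mosquito infection rate ratio. If positives are too few to fit the model, MIR will be reported by arm with its interval and no efficacy claim will be made.

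The link and offset follow from the pooling: the chance that a pool is positive is 1 − (1 − π)^m, so log(−log(1 − that chance)) equals log m plus a term in π alone.

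An acceptable equivalent is the count of positive pools per cluster in a negative binomial model with offset log(mosquitoes tested). One check of that model, with 150 trials, log-SD 1, mean 2 and 10 per 1,000, gave 10% null rejection, so sparse data need care there too.

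The cost is a short SAP edit and a little code; pools, laboratory data and R package stay the same. The limits should be stated: power stays low with few positives, and little is gained if infection varies strongly between clusters.
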